**SECTION IX: DATA PROTECTION PLAN**

78. Is the private information being requested the minimum necessary to meet the research goals?

Yes       No       N/A

79. What records or data will you be using or collecting? Check all that apply:

- New data for this study
- Data already collected for another research study
- Data already collected for administrative purposes
- Medical records; approximately how many records: **150**
- Electronic information from clinical database
- Other:

80. Will any sensitive information be collected, such as information regarding sexual behavior, HIV status, recreational drug use, illegal behaviors, physical abuse, mental health disorders, etc.?

- Yes
- No

- If yes, what sensitive information will you be collecting?
- If yes, will you be obtaining a Certificate of Confidentiality?  Yes  No

81. Where will data be stored? Please note that **no other storage options are permitted**, including the use of Carilion provided or personal laptops, encrypted flash drives or other portable devices. Data must not be placed in a cloud or other hosted environment. Any exceptions must first be approved by the Carilion Privacy and Information Security Officer and documentation provided to the IRB.

Please check all that apply:

- Hardcopy data in a locked office in a locked cabinet
- Electronic data on a password protected, secure drive on a Carilion server (contact [[contact]](mailto:[contact]) to set up a shared drive)
  - Select the software to be used:  Excel  Access  Other: Describe Qualtrics
- REDCap (contact [[contact]](mailto:[contact]) to discuss use of REDCap). If all data, including the code link, will be stored in REDCap, skip to #82.

82. The standard at Carilion to protect identifiable data used in research is to use a code and link system. Two files should be kept in two separate secure locations. One file should use a unique code for each subject in connection with any sensitive or health information. The other file (the link) associates the unique code with subject identifiers (e.g. name, medical record number). Please describe how you will store data using the options below.

- Retrospective Record Review Research Only:** The master list will contain direct subject identifiers such as name and MRN along with a unique subject code. It will be stored separately from the coded research data set at all times. The research data set will not include any HIPAA identifiers with the exception of a date.
- Prospective Collection of Data**, including surveys or collection of new data: While initial collection of research data may contain identifying information, it must be stored using a code linked to the subject's identity using a master list, or will include only anonymous or de-identified data. All HIPAA identifiers will be stripped from the initial research data collection data tools and replaced with a unique subject code.
- Prospective Collection of Sensitive Data**, including surveys or collection of new data: Research data will be linked to identifiers by a unique subject code at all times. The code will be linked to a master list that contains identifying information. The master list and coded research data will be stored in separate locations.

83. Please describe how you plan to protect identifying information from improper use and disclosure by answering the questions below.

- a) Who will have access to identifiers? **Trained study team personnel**
- b) How will you limit access to the identifiers? **Identifiers will be stored separately on a password protected master list in Carilion Red Cap or on a Carilion server.**

84. When will study files, including informed consent documents, study documents, and the code link with identifiers be destroyed?

Please note that you must retain research records for the greater of:

- At least three years after completion of the research.

- If the study involves Protected Health Information, research records must be maintained for a minimum of six years after the completion of the research.
- For drug studies conducted under an IND, two years following the date a marketing application is approved for the drug for the indication for which it is being investigated; or, if no application is to be filed or if the application is not approved for such indication, until two years after the investigation is discontinued and FDA is notified.
- For device studies conducted under an IDE or abbreviated IDE, two years after the latter of the following two dates: The date on which the investigation is terminated or completed, or the date that the records are no longer required for purposes of supporting a premarket approval application or a notice of completion of a product development protocol.
- The retention period required by the sponsor
- The retention period required by local, state, or international law.
- The retention period required by a site that is not part of Carilion Clinic.

**10** Years after the study has been closed with the IRB (enter # of years)

Other (please specify):

## SECTION X: MEDIA USE

85. Will any media be used to record subjects' voice or image?

Yes       No

- If yes, describe what media will be used, how the media will be used, and justify why it is necessary to use the media to collect data:

86. Will the subjects' voice or image be recorded without their knowledge?

Yes       No

- If yes, describe the deception and the debrief procedures:

## SECTION XI: SAFETY & MONITORING

87. Describe the process for dealing with adverse events and unanticipated problems.

**We do not anticipate any adverse events/unanticipated problems, but these will be reported to the IRB immediately upon occurrence**

88. Is there a Data Safety Monitoring Board or other safety oversight committee?

Yes       No

- **If yes:**

What is the name of the board or committee?

If the DSMB is local, please name the members.

How frequently will the data be reviewed for safety?

Every 3 months       Every 6 months       Annually       Other:

- **If no:**

How will the data be monitored to ensure the safety of subjects? **The proposed study poses minimal risk to patients, and therefore no safety monitoring is required.**

89. Are there plans for visits by sponsor monitors or auditors to review study documents for regulatory requirements?

Yes       No       N/A

- If yes, Identify the group that will be conducting the monitoring/auditing visit(s) and the number of times you anticipate this occurring over the next year:

90. Does this project involve research using any of the following?

|                              |  |   |
|------------------------------|--|---|
|  Yes |  No | Mammalian cell/tissue culture (includes established cell lines or primary isolation of cell lines from tissue, blood, etc.)                                     |
|  Yes |  No | Cultivated microorganisms (isolated, grown in vitro and used for non-diagnostic research, i.e. isolation of biohazardous organisms from patient samples) |
|  Yes |  No | Research animals  |
|  Yes |  No | Molecular cloning, recombinant DNA or gene therapy techniques   |

**If you checked yes on any of the above boxes, you are required to contact the Carilion Clinic Research Safety Committee at [name] for important guidance.**

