**-EFT/Control engagement (Weeks 3-16).**

Beginning in Week 2, participants will be randomly assigned to either the EFT+BT or BT control groups. Participants in the EFT+BT group will be asked to generate episodic cues similar to the tasks used in our previous studies on EFT's effect (Daniel et al., 2013). Participants will list and describe events for different time periods. The episodic component of the thinking task will occur while the participants are asked to describe what they are imagining about each event (e.g., vacations, weddings, parties, health goals, etc.). EFT participants will list positive future events they are looking forward to and list events that could happen at different general future time points (e.g., 1 month, 2-6 months, 7-12 months). Participants will also create text-based cues for each event, which will consist of descriptions of the future event (e.g., "In about 6 months, I am attending my sister's wedding in Montana. I am enjoying the crisp air and getting to see my family again."). In contrast, the BT control group will not generate these events.

For the remainder of the intervention, participants in both groups will be sent text-based prompts via cell phone to access the study website (built in Qualtrics survey software). Once accessed, the study website will guide EFT+BT participants to engage in EFT by presenting cues. Brief questions may also be presented asking participants to describe their study experience (e.g., "Have you encountered any diet or activity challenges today?"). Participants in the BT control group will only be prompted to access the study website to answer these questions.

Experimenters will train participants in both groups on how to access the study website from their cell phone or alternative internet accessible device (e.g. laptop, tablet, desktop computer), as well as how to pay attention to and think about the cues, and how to adhere to the study's expectations for utilizing the cues (EFT+BT group only). Participants may be prompted several times a day to access the website and, for the EFT+BT group, instructed to use their cues any time that need to, especially around eating episodes.

At the end of the intervention period (approximately Week 16), participants will retain access to educational and other materials in Qualtrics through Week 24. However, participants will not be provided with prompts to access these materials during this period and will not be required to use the website.

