#### **SECTION IV: RISKS AND BENEFITS**

25. Summarize the possible risks to subjects and how they have been minimized in the study design. Include risk of psychosocial harm (e.g., emotional distress, embarrassment, breach of confidentiality), economic harm (e.g., loss of employment or insurability, loss of professional standing or reputation, loss of standing within the community) and legal jeopardy (e.g., disclosure of illegal activity or negligence), as well as known side effects of study medication, if applicable, and risk of pain and physical injury. Define the level of risk (minimal risk, risk but with potential benefit to patient, risk but no benefit to patient). Describe any procedures that will be used to prevent or minimize risks or discomforts. Note: Most studies create at least a small risk of breach of confidentiality or privacy.

**Overall, the risks of study participation are minimal. Participants will be informed of the risks associated with the study.**

**In subjects who are enrolled with an A1c between ~8% and 9.9%, an A1c over 10% will trigger a notification of their physician or appropriate medical referral. In**

**subjects who are enrolled with an A1c  $\geq 10\%$ , any 1 percentage point increase over baseline will trigger a notification of their physician or appropriate medical referral.**

**Participants will be free to withdraw from the study at any time, and their refusal to continue will not affect other medical care provided at any healthcare facility.**

**Participants might feel uncomfortable disclosing some personal information such as medical history. Participants might experience adverse effects associated with changes in diet, including feeling hungry, fatigue, or headache.**

**Participants may, if they are on sulfonylurea or glinide medications, experience symptoms associated with hypoglycemia. Given that insulin use is an exclusion for this study, this is likely to be an uncommon and mild clinical issue. Participants will be instructed to discuss the possibility of hypoglycemia with their treating physician and the case managers will educate participants about hypoglycemic reactions and advise those on hypoglycemic medications to carry an additional source of ready sugar.**

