**\*\*\*If this study is a retrospective record review only, you may skip to Section VII\*\*\***

31. Will subjects receive any compensation or gifts to participate?

Yes       No       N/A

- If yes, specify payment amount, how it will be prorated and how payment will be made: **Participants may receive up to \$300 for completion of all study procedures, as follows.**
  - **Assessment Session 1 (Week 0): \$20**
  - **Assessment Session 2 (Week 8): \$30**
  - **Assessment Session 3 (Week 16): \$35**
  - **Assessment Session 4 (Week 24 follow-up, post-intervention): \$40**
  - **Physical Activity and Diet Assessments 1-3 (Weeks 0, 8, and 16): \$20 per assessment week (\$60 total possible). These will occur outside the laboratory. At each assessment, participants will be asked to wear the Actigraph accelerometer to measure physical activity for a period of seven days. On three of those days, participants will also be asked to complete the ASA-24 dietary recall questionnaire online.**
  - **Brief Online Assessments (Weeks 3, 9, and 15). \$5 per assessment (\$15 total possible). Participants will be asked to complete brief online assessments (e.g., delay discounting, food purchasing) outside of the laboratory. EFT+BT participants will also be asked to complete an EFT event/cue-generation exercise.**
  - **Participants will also receive an additional bonus at Week 24 of \$100 for completing 90% or more of all assessment sessions and at-home assessments (Actigraph, brief online assessments, and diet recalls). The magnitude of this bonus was chosen in order to motivate attendance at the follow-up assessments for the majority of participants and thus minimize the occurrence of missing data, including from those participants who may have been less successful in the intervention or follow-up period.**

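### Section XI says no safety monitoring is required although Section IV sets HbA1c notification rules, and the available text describes no routine question that would find hypoglycemia or other adverse events

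*Combined protocol and SAP*

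**What the plan says.** Section XI, item 88 asks whether there is a safety board and, if not, how the data will be monitored for subject safety. The answer in the second field is "The proposed study poses minimal risk to patients, and therefore no safety monitoring is required". Item 87, on handling events, reads "We do not anticipate any adverse events/unanticipated problems, but these will be reported to the IRB immediately upon occurrence".

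Section IV, item 25 says more. For participants enrolled with HbA1c of about 8% to 9.9%, "an A1c over 10% will trigger a notification of their physician or appropriate medical referral". For those enrolled at 10% or more, "any 1 percentage point increase over baseline will trigger a notification of their physician or appropriate medical referral". It also says "Participants might experience adverse effects associated with changes in diet, including feeling hungry, fatigue, or headache" and names hypoglycemia as possible for those taking sulfonylureas or glinides, with the comment "Given that insulin use is an exclusion for this study, this is likely to be an uncommon and mild clinical issue".

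Item 25 gives three measures against hypoglycemia. Participants are told to raise it with their own physician, case managers teach them about reactions, and those on drugs that can cause it are advised to keep sugar with them.

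**The concern.** The safety section and the risk section do not agree. One says nothing will be monitored and no events are expected. The other commits the study to acting on HbA1c values and lists events that may occur. A reader who consults only Section XI would not learn of the HbA1c rules.

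The more practical matter is how events come to light. Item 87 says where an event goes once it is known, not how anyone learns of it. Every participant is prescribed or recommended an oral glucose-lowering drug (item 21), sulfonylureas and glinides are not excluded, and everyone is coached on diet (item 22). Item 19 hypothesizes larger dietary and medication-adherence gains with EFT. If hypoglycemia or diet-related symptoms did occur, they could differ by arm, and reports that participants happen to volunteer would be a weak basis for comparing the arms.

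**Working it through.** The plan gives no figure to reproduce on this point. The check sets the text side by side, then counts the contacts at which a question could be asked.

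**1. What item 88 is answering.** The sentence sits in the field for studies without a committee, which asks what is done instead. Item 25 already supplies an answer: the HbA1c rules. HbA1c is measured at Weeks 0, 8, 16 and 24 (item 22), so the rules can operate at three post-baseline visits.

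**2. What the HbA1c rules can detect.** Apply them to sample values, reading the second rule as a rise of 1 point or more:

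| Baseline HbA1c | Later HbA1c | Notification? |
|---|---|---|
| 8.0% | 10.0% | No |
| 8.0% | 10.1% | Yes |
| 10.0% | 10.9% | No |
| 10.0% | 11.0% | Yes |
| 9.0% | 5.0% | No |
| 12.0% | 5.5% | No |

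Both rules look upward only. They cover worsening control and cannot signal hypoglycemia.

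**3. Whether anything else asks.**
- The measures in item 23 include an eating-disorder scale with referral, a depression questionnaire and a medication-adherence questionnaire. No hypoglycemia or adverse-event question is described.
- Case-management content (item 22) covers diet, activity, adherence and problem solving. Item 25 adds education about hypoglycemia. Neither describes asking about events or recording them.
- On the study website, "Brief questions may also be presented asking participants to describe their study experience". The example given concerns diet or activity challenges.
- At Weeks 3, 9 and 15, "Participants will be asked to complete brief online assessments (e.g., delay discounting, food purchasing) outside of the laboratory" (item 31). The examples are not about symptoms.

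**4. Item 87 against item 25.** Item 87 anticipates no events, while item 25 lists several. Item 87 also sends all events to the IRB at once, with no distinction by seriousness or expectedness.

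**5. Contacts already planned.** Calls are weekly in about Weeks 1 to 8, then bi-monthly to Week 16. Bi-monthly over those 8 weeks could mean one call (every two months) or four (twice a month).
- Calls: 8 + 1 = 9 to 8 + 4 = 12.
- With the visits at Weeks 8, 16 and 24: 9 + 3 = 12 to 12 + 3 = 15 staff contacts per participant.
- Calls stop at about Week 16, so from then to Week 24 the only remaining staff contact is the Week 24 visit.

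**6. Recording burden.** With 54 completers and the 15% attrition in item 24, randomized N = 54 / 0.85 = 63.5, about 64.
- Upper end, all 64 attend everything: 64 x 15 = 960 entries.
- Lower end, all 10 dropouts leave before the first contact: 54 x 12 = 648 entries.

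**The case against.** The strongest reply is that item 88 follows a question about a committee, so its author may have meant only that a minimal-risk study needs no formal data review. The HbA1c rules are individual referral rules, and they stand whatever item 88 says. Item 25 also refers to monitoring procedures long in use by the group. This largely stands: rewording item 88 alone changes nothing for any participant. The field nonetheless asks what replaces a committee, and the literal answer is nothing.

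The second reply is that hypoglycemia is handled separately. Participants are taught what to recognize, told to speak to their physician and advised to carry sugar, and they talk to the same case managers weekly for about eight weeks. The protocol expects the problem to be uncommon and mild because insulin users are excluded. This stands as mitigation. A reader might infer that participants are left unprotected against hypoglycemia, and the documents do not support that. Education and advice do not, however, produce a record.

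Third, the absence of a question rests on material not seen. Appendix D (measures), Appendix B (manual), the data-collection tools and the consent form were not available. A reader might infer that the study has no adverse-event question at all. Only the narrower statement is supported: the available text describes none.

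Fourth, item 87 as written is over-inclusive, which errs on the safe side. Loosening it for mild hypoglycemia would weaken reporting of the very risk at issue, with mild undefined and the IRB's own policy not in view. That objection is right, and the fix below respects it.

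**Conclusion.** The point holds as a low-priority gap in safety ascertainment. Two parts are settled by the text: items 87 and 88 do not match item 25, and the HbA1c rules detect only high or rising values. The third part, that no systematic question finds or records hypoglycemia or other events, holds for the available text and depends on what the unseen appendices and forms contain.

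The size in missed events cannot be given, because the documents state neither an event rate nor the share of participants on sulfonylureas or glinides. For the same reason a reader should not take the arm size as the basis for a hypoglycemia bound. Item 25 confines that risk to users of those drugs, so a limit computed on whole arms would look tighter than the data allow.

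No efficacy result or power figure is affected, and the documents do not support a claim that the trial is unsafe or needs a safety board. The contact count assumes the schedule in item 22 is followed.

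**What to change.** 1. In item 88, cite the item 25 HbA1c checks and notifications at Weeks 8, 16 and 24 as the monitoring procedure.
2. First check Appendix D and the data-collection forms. Unless one already does so, ask both arms one fixed, identically worded question on hypoglycemia symptoms and other adverse events at the existing case-management calls and the Week 8, 16 and 24 visits. Tabulate the answers and the HbA1c notifications by arm, descriptively and without a test.
3. In item 87, keep immediate reporting for serious or unanticipated events and for any hypoglycemia. Log only expected hunger, fatigue and headache for periodic summary, subject to the IRB's own policy. Without this step, each solicited report of hunger or headache could call for an immediate IRB report.

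The cost is a few lines of wording, one question, one table and about 648 to 960 short log entries across the trial, with no added visits and no change to any clinical rule. Case managers would have to separate expected effects from reportable ones. They also know the arm, since they instruct participants in EFT or the control task, so identical wording reduces reporting bias but does not remove it. The table should say so.

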## SECTION XII: STORED DATA AND HUMAN BIOLOGICAL MATERIALS REPOSITORIES

Databases and specimen repositories, also known as registries or banks, are used to store data and/or specimens for future use. When the use is for clinical purposes or quality improvement, IRB approval is not required. However, when the use is for research purposes, the databases/repositories must be approved by the IRB (45 CFR 46 and 45 CFR 160 & 164).

91. Will this research collect and store data/specimens (blood, urine, biopsy tissue, saliva, etc.) for future research beyond the parameters of this study?

|                              |  |
|------------------------------|--|
|  Yes |  No |
|------------------------------|--|

**\*\*\*If no, you may skip the remainder of this section and go directly to Section XIII\*\*\***

92. Will the data/specimens collected for this research be stored in an existing repository at Carilion that is used for future research?

|                              |                             |
|------------------------------|-----------------------------|
|  Yes |  No |
|------------------------------|-----------------------------|

- If yes, provide repository name:

93. Will the data/specimens collected for this research be stored in a non-Carilion repository that is used for future research?

|                              |                             |
|------------------------------|-----------------------------|
|  Yes |  No |
|------------------------------|-----------------------------|

- If yes, attach a protocol or other information describing the repository operations.

94. Will the data/specimens collected be stored in a repository for future research that will be developed and operated by the researcher(s)?

|                              |                             |
|------------------------------|-----------------------------|
|  Yes |  No |
|------------------------------|-----------------------------|

- If yes, you must also submit a Specimen/Data Repository Application to the IRB

